## 1 Responsible Parties Involved in the Study

#### 1.1 Location of Information

Investigator and Responsible Party information for this multi-center clinical investigation is on file at the operating company

4 MAR 2022; Version Rev 3 DSJ-2019-02 Confidential

Page 4 of 47 TV-eFRM-02920

## **3 STUDY SUMMARY**

## 3.1 Protocol Synopsis

Clinical Sponsor	DePuy Synthes Joint Reconstruction
Title	Multi-Center, Non-Controlled, Prospective Radiostereometric Analysis of the PINNACLE ® Dual Mobility Construct
Short Title	PINNACLE® DM RSA Study
Protocol Number	DSJ 2019 02
Indication	Total Hip Arthroplasty (THA)
Study Article Description	PINNACLE ® Acetabular Cup, PINNACLE ® CoCrMo Dual Mobility Metal Liner, a BI-MENTUM ™ ALTRX ® Dual Mobility Polyethylene Liner, a DePuy femoral stem with a polished femoral neck and a DePuy modular, femoral head PINNACLE ® Dual Mobility Metal Liners and Porous-coated PINNACLE ® Acetabular Cups are intended for cementless applications.
Study Design	Multi-Center, Non-randomized, Non-Controlled, Prospective
Study Population	Males and Females aged 21 or older, who are undergoing primary, unilateral THA or revision THA and who may have, in the opinion of the Investigator, a risk of dislocation in the operative joint.
Number of Subjects	N = a minimum of 30 and up to 45
Number of Sites	3 (all Canadian)
Enrollment Timeframe	12 months
Subject Follow-Up	Subjects will be seen at the following intervals: Preoperative, operative, 6 weeks, 3 months, 6 months, 1 year and 2 years postoperatively
Study Objectives	
 
To establish the mean subsidence profile of the PINNACLE® Acetabular Shell and Dual Mobility Metal Liner construct using model-based RSA over the first two years post-implantation
 
To compare study results from this trial to historical PINNACLE® data obtained from DSJ 2018 02.
 

Endpoints	
 
Primary: 
 
RSA measured mean superior cup migration (subsidence: Y translation in mm) at 2 years
 
Secondary: 
 
Comparison of mean superior cup migration at 2 years to historical PINNACLE® data
 
RSA measured subsidence of the PINNACLE® Acetabular Shell at 3 months, 6 months and 1 year and compare to historical PINNACLE® data
 
 
 
 
 

Page 6 of 47

	
 
Other RSA measurements (X and Z translations in mm, X, Y, and Z rotations in degrees, and maximal total point motion in mm) at all time points and compare to historical PINNACLE® data
 
Linear head penetration at 6 weeks, 1 year and 2 years and compare to historical PINNACLE® data
 
Functional and health status as measured with Harris Hip Score, HOOS Jr. and Forgotten Joint Score (FJS-12) and compare to historical PINNACLE® data at baseline and 3 months, 6 months and 1 and 2 years post-operative
 

	
 
Exploratory:
 
Subsidence for subset of Subjects where RSA data was obtained prior to discharge and compare to historical PINNACLE® data
 
Analyses to examine the correlation of functional and
 

	
 
health status outcomes vs. RSA observations may be explored
 
Incidence of intraprosthetic dislocation (IPD)
 

	Incidence of intraoperative complications
	
 
The type and frequency of any serious and non-serious device or procedure-related AEs across all study intervals will be summarized
 

Inclusion Criteria	
 
Individuals requiring THA for a severely painful and/or disabled joint (typically due to non-inflammatory degenerative joint disease); failed previous hip surgery; or dislocation risks.
 

	2. Individuals who are able to speak, read and comprehend the informed patient consent document and willing and able to provide informed patient consent for participation in the study and have authorized the transfer of his/her information to DePuy Synthes
	3. Individuals who are willing and able to return for follow-up as specified by the study protocol
	4. Individuals who are a minimum age of 21 years at the time of consent
	
 
Individuals who are willing and able to complete the Subject Hip Outcomes questionnaires as specified by the study protocol
 

Exclusion Criteria	1. Individuals who have an active local or systemic infection

Page 7 of 47

2.	Individuals who have loss of musculature, neuromuscular compromise or vascular deficiency in the affected limb rendering the procedure unjustified.
3.	Individuals with poor bone quality, such as osteoporosis, where, in the surgeon's opinion, there could be considerable migration of the prosthesis or a significant chance of bone fracture and/or the lack of adequate bone to support the implant(s)
4.	Individuals with Charcot's or Paget's disease
5.	Individuals who, in the judgement of the investigator, would not be a candidate for protocol allowable components to be used for their THA
6.	Women that are pregnant or lactating
7.	Individuals who have had a contralateral hip that was implanted less than 6 months prior to the time of consent into this study or individuals that expect to have a contralateral hip implanted in the 6 months following the time of consent into this study
8.	Individuals that have amputations in either leg that would impact rehabilitation following surgery
9.	Individuals who are bedridden per the Investigators determination.
10.	Individuals that have participated in a clinical investigation with an investigational product (drug or device) in the last three months
11.	Individuals currently involved in any personal injury litigation, medical-legal or worker's compensation claims
12.	Individuals, in the opinion of the Investigator, who are drug or alcohol abusers or have psychological disorders that could affect their ability to complete patient reported questionnaires or be compliant with follow-up requirements
13.	Individuals diagnosed and taking prescription medications to treat a muscular disorder that limits mobility due to severe stiffness and pain such as fibromyalgia or polymyalgia
14. 15. 16.	Subject has a medical condition with less than 2 years life expectancy Individual has a BMI ≥45 kg/m  . Individuals who require revision arthroplasty and have a well-fixed non-DePuy Synthes femoral stem or a well-fixed DePuy Synthes femoral stem that does not have a polished neck

Safety Assessments	Type and frequency of device or procedure related Adverse Events will be collected. The Site Ethics Committee/Research Ethics Board (REB) will provide oversight for study Subject safety.
Sample Size	The purpose of this study is to summarize the mean subsidence (superior cup migration) of the acetabular shell as measured with RSA. Mean subsidence will be summarized at all time points; there are no hypotheses in this study. The standard deviation in observed migration values at 2 years post-op is anticipated to be approximately 0.2 mm. Based upon this standard deviation, a sample size of N=30 is anticipated to provide a 95% confidence interval for comparison with historical PINNACLE ® data with a margin of error of approximately $2(0.2/\sqrt{30}) = 0.073$ mm, which is deemed to be an adequate level of precision by the Sponsor. Up to 45 Subjects may be enrolled to offset pre and post-operative attrition.
Statistical Analysis	There are no formal hypothesis tests for this study. Summary statistics of primary, secondary and exploratory outcomes will be provided, along with 95% confidence intervals. Comparisons of the primary and secondary endpoints with historical PINNACLE ® data will be conducted using the t-test and the Fisher's exact test. Those comparisons will only be provided to facilitate clinical judgement.
Interim Analysis	An interim analysis will be conducted when all Subjects have reached 1-year post-op in order to give product development an understanding of acetabular cup subsidence that might be expected for future product development purposes and support regulatory submissions. There is no intention to utilize this interim analysis as a means to justify stopping the study early.
Determination if DMC/CEC	Not Required
Time and Events Schedule	See below

I         I         I>/>         I         I
> > >  >
> >
ļ
$\mathbf{i}$
>
C M/D
>
. >
· >

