## 5 PURPOSE

## 5.1 Primary Objective and Endpoint

The primary objective is to establish the mean superior cup migration of the PINNACLE® Dual Mobility Construct using model-based RSA over the first two years post-implantation. The primary endpoint is the mean vertical subsidence (Y translation, also known as superior cup migration) at 2 years as measured with RSA. Additionally, the data from this study will be compared to historical PINNACLE® data obtained in study DSJ\_2018\_02.

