#### 11.7 Levels of Significance

There are no specific hypotheses being tested in this study. To facilitate clinical interpretation, confidence intervals will accompany primary and secondary endpoint estimates and will be 2-sided 95% confidence intervals; these confidence intervals are considered to be exploratory.

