#### 11.8 Sample Size Justification

This study sample size was established to provide adequate precision on the mean subsidence estimate at 2 years. A common standard deviation of 0.2 mm is anticipated. Based upon this standard deviation and a sample size of N=30, a 2-sided 95% confidence interval is anticipated to have a margin of error equal to approximately  $2SE = 2 \times \frac{SD}{\sqrt{n}} = 2 \times \frac{0.2}{\sqrt{30}} = 0.073$  mm. This margin of error was deemed to be an adequate level of precision by the Sponsor.

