#### 11.12.4 Comparisons to Historical PINNACLE® Data

All primary, secondary, and exploratory endpoints will be compared to their counterparts in the DSJ\_2018\_02 (PINNACLE® RSA) study for the visits at which those endpoints are assessed using the t-test if the endpoint is continuous or Fisher's exact if the endpoint is categorical. The mean difference (PINNACLE® – PINNACLE® DM), the 2-sided 95% confidence interval for the difference, and the p-value for the test of equality will be presented. There are no formal hypotheses associated with those tests and the p-values and confidence intervals are only presented to facilitate clinical judgment.

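### The synopsis gives 0.073 mm as the margin for the comparison with historical PINNACLE data, but that is the margin for this study's own mean; the planned difference will be less precise

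*Combined protocol and SAP*

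**What the plan says.** The protocol states its sample-size rationale twice, with the same formula and the same result.

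- **Section 3.1, Sample Size row.** "The standard deviation in observed migration values at 2 years post-op is anticipated to be approximately 0.2 mm". On that basis "a sample size of N=30 is anticipated to provide a 95% confidence interval for comparison with historical PINNACLE" data, with a margin of 2(0.2/√30) = 0.073 mm, which the Sponsor considers precise enough. The row adds: "Up to 45 Subjects may be enrolled to offset pre and post-operative attrition".
- **Section 11.8.** "This study sample size was established to provide adequate precision on the mean subsidence estimate at 2 years". On variability, the section says: "A common standard deviation of 0.2 mm is anticipated", and the same 2×SE calculation at N=30 gives 0.073 mm, again accepted by the Sponsor. The historical comparison is not mentioned.

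The comparison itself is specified in section 11.12.4. Continuous endpoints are compared with DSJ_2018_02 by t-test, and along with the mean difference "the 2-sided 95% confidence interval for the difference, and the p-value for the test of equality will be presented". Section 5.1 says of the primary objective: "Additionally, the data from this study will be compared to historical PINNACLE" data. The synopsis lists this comparison as a study objective, and lists the 2-year comparison as the first secondary endpoint.

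**The concern.** The two statements attach one number to two different quantities. In section 11.8, 0.073 mm is the precision of this study's 2-year mean. In the synopsis it is the precision of the comparison with the earlier study. The formula contains one SD and one n, both belonging to this study, and has no term for the uncertainty in the DSJ_2018_02 mean. It cannot be the margin for the interval that section 11.12.4 plans.

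The study has no hypotheses and no power claim, so interval width is its only sample-size justification. The synopsis records the Sponsor's acceptance of 0.073 mm for a stated objective that will not have that precision at N=30. No other section gives a margin for the difference. A reader of the synopsis would therefore expect the comparison to resolve smaller differences in migration than it can.

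**Working it through.** **Inputs from the documents**
- SD of 2-year migration: 0.2 mm (sections 3.1 and 11.8)
- n in this study: 30 (sections 3.1 and 11.8)
- Two-sided 95% interval, multiplier 2 (sections 11.7 and 11.8)
- Comparison: t-test and interval for the mean difference (section 11.12.4)

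**Inputs that must be assumed**
- Historical sample size, m, and historical SD, s. Neither is given for DSJ_2018_02. Section 11.8 calls the 0.2 mm SD common without saying common to what. The base case takes s = 0.2 mm.

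**Step 1: reproduce the plan's figure.** One mean: 2 × SD/√n = 2 × 0.2/√30 = 0.0730 mm. This matches. Exact quantiles give 0.0716 mm (normal) and 0.0747 mm (t, 29 df).

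**Step 2: margin for the difference on the same 2×SE basis.** The formula is 2√(0.2²/30 + s²/m). With s = 0.2 it becomes 0.4√(1/30 + 1/m), and its ratio to the stated margin is √(1 + 30/m).

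| Assumed m | Margin for difference (mm) | Excess over 0.073 mm |
|---|---|---|
| 20 | 0.115 | 58% |
| 30 | 0.103 | 41% |
| 45 | 0.094 | 29% |
| 60 | 0.089 | 22% |
| 100 | 0.083 | 14% |
| 200 | 0.078 | 7% |

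Since 1/m is positive for every finite m, the margin is always above 0.073 mm. It falls to 0.073 mm only in the limit where the historical mean is treated as known without error.

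**Step 3: vary the historical SD at m = 30.** Here the margin is 2√((0.04 + s²)/30).
- s = 0.1: 0.082 mm
- s = 0.3: 0.132 mm
- s = 0.4: 0.163 mm

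**Step 4: does the ceiling of 45 subjects recover the figure?** If all 45 were evaluable, with SD 0.2 mm in both studies, the margin is 0.4√(1/45 + 1/m): 0.094 mm at m = 30 and 0.084 mm at m = 45. Setting it equal to 0.4√(1/30) requires 1/m = 1/30 − 1/45 = 1/90, so m = 90. With equal groups, 0.073 mm needs 60 per study, since 0.4√(2/60) = 0.0730.

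**Step 5: sensitivity to the multiplier.** At m = 30 the difference margin is 0.101 mm with the normal quantile and 0.103 mm with t (58 df). With exact quantiles it drops just below 0.073 mm only for a very large historical sample (t: 0.0727 mm at m = 1000).

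**The case against.** The strongest reply is that nothing is miscalculated. The Sample Size row opens by describing the study's purpose as summarising mean subsidence, prints a one-sample formula, and never mentions an interval for a difference. It could mean only that this study's interval will be set beside the historical result, in which case 0.073 mm is correct. Section 11.8, the full statement, attaches both the figure and the Sponsor's acceptance to the single mean, so nothing shows that N was chosen on a wrong margin. The intervals "will be 2-sided 95% confidence intervals; these confidence intervals are considered to be exploratory" (section 11.7), no decision rule uses 0.073 mm, and the true width for the difference will be reported. The size of the discrepancy depends on historical data that are not in the documents.

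Much of this stands. The arithmetic is right, section 11.8 needs no correction, the consequence is limited, and only the direction is established from the documents alone. The alternative reading does not stand. Section 11.12.4 plans an interval for the difference, and the synopsis's own Statistical Analysis row says the comparisons use the t-test. Neither treats the historical value as a fixed constant. The descriptive status does not remove the point either, because precision is the only justification offered for the sample size.

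It could also be said that deleting the reference to the comparison would be enough. That would remove the contradiction, but it would leave a stated objective with no planning precision at all.

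**Conclusion.** The concern holds. The synopsis assigns a one-sample margin of 0.073 mm to a two-sample comparison, and it disagrees with section 11.8 about what the figure describes. On the protocol's 2×SE rule with 30 subjects, the direction is certain: the comparison is less precise than stated.

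The size is conditional. With an SD of 0.2 mm in both studies and 20 to 100 historical subjects, the margin is 0.115 to 0.083 mm, which is 58% to 14% above the stated value. With 30 historical subjects and a historical SD between 0.1 and 0.4 mm, it is 0.082 to 0.163 mm. These historical inputs are assumptions.

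The statement should be corrected, but the impact is moderate. The single-arm primary summary is unaffected, and no formal inference rests on the comparison.

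**What to change.** 1. In the Sample Size row of the synopsis, attach 0.073 mm to the single-arm estimate only, in line with section 11.8: 30 subjects evaluable at 2 years are expected to give a two-sided 95% interval for mean subsidence with a margin of about 0.073 mm. Naming the evaluable number is a small addition to section 11.8. It makes explicit the n on which the margin depends, since section 11.12.1 analyses only subjects with both 6-week and 2-year data. The sentence on enrolling up to 45 to cover attrition can stay.
2. State the expected margin for the difference separately, as 2√(0.2²/30 + s²/m), using the evaluable 2-year sample size and SD of DSJ_2018_02. If these are not yet known, give a range such as the one above, with its assumptions.
3. Say whether the Sponsor also considers that margin adequate.

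The cost is one reworded sentence, one added figure or range, and a short statement of adequacy. Enrolment, conduct, analysis and the figure in section 11.8 are unchanged. The stated precision for the comparison will be less favourable.

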3.2 TIME AND EVENTS SCHEDULE

\* ROM optional at 6 weeks only

\*\* As Needed, ^ At able center(s) only, \*\*\* As Applicable, ^^ Double exam obtained if not prior

4 MAR 2022; Version Rev 3 DSJ-2019-02 Confidential

TV-eFRM-02920

Page 10 of 47

## **4 INTRODUCTION**

#### 4.1 Background

Hip replacement, or arthroplasty, is a surgical procedure in which the diseased or damaged parts of the hip or hip joint are removed and replaced with prosthetic implants in the proximal femur (stem) and the acetabulum (cup or shell). The most common reason that people have hip replacement surgery is the wearing out of the hip joint as a result of osteoarthritis. Other conditions, such as rheumatoid arthritis (a chronic inflammatory disease that causes joint pain, stiffness and swelling), avascular necrosis (loss of bone caused by insufficient blood supply), injury (such as fracture), and bone tumors also may lead to breakdown of the hip joint and the need for hip replacement surgery.

#### 4.2 Radiostereometric Analysis (RSA)

Radiostereometric Analysis is an accurate method of determining the migration of orthopaedic implants following surgical procedures such as total hip arthroplasties. RSA is able to measure early micromotion of the hip implant which is predictive of long-term fixation.

There are no RSA evaluations of the PINNACLE® Dual Mobility Metal Liner. Therefore, in order to evaluate future dual mobility hip replacement products, baseline migration values for the PINNACLE® Dual Mobility Implant will be determined; in addition, PINNACLE® Dual Mobility RSA data will allow for comparison with historical RSA data obtained using standard PINNACLE® acetabular constructs in study DSJ\_2018\_02.

#### 4.3 Study Article Description

The PINNACLE® Dual Mobility Metal Liner is intended to be used in total hip arthroplasty with a PINNACLE® Acetabular Cup, a BI-MENTUMTM ALTRX® Dual Mobility Polyethylene Liner, a DePuy femoral stem with a polished neck and a DePuy modular, femoral head. The dual mobility liner is a CoCr device that forms a modular connection with the acetabular shell and serves an articular surface for the polyethylene liner. PINNACLE® Dual Mobility Metal Liners and Porous-coated PINNACLE® Acetabular Cups are intended for cementless applications. All Subjects will receive a PINNACLE® Dual Mobility metal liner and a BI-MENTUMTM ALTRX® Dual Mobility Polyethylene Liner in this study.

#### 4.4 Benefits/Risks

#### 4.4.1 Benefits

The primary goal of total hip arthroplasty is the anatomic reconstruction of the hip joint, resulting in favorable prosthetic joint load and function. Mechanically, the goals are to create a stable articulation with an optimized range of motion, restore biomechanics for muscular efficiency and equalize limb lengths.

4 MAR 2022; Version Rev 3 DSJ-2019-02 Confidential Page **11** of **47** TV-eFRM-02920

#### 4.4.2 Risks

As specified in the Instructions For Use (IFU-0902-00-898 and IFU-78410403 included in the implant packaging), the following are generally the most frequently encountered adverse events and complications in total hip arthroplasty, including the study devices:

GENERAL

- Change in position of the prosthetic components
- Early or late loosening of the prosthetic components
- Fatigue fracture of the femoral stem
- Excessive wear or fracture of the bearing components
- Early or late infection
- Peripheral neuropathies. Subclinical nerve damage may also occur as a result of surgical trauma
- Tissue reactions, osteolysis, and/or implant loosening caused by metallic corrosion, allergic reactions, wear or particulate debris
- Pain

#### INTRAOPERATIVE

- Acetabular fracture
- Femoral shaft perforation, fissure or fracture, which may require the use of internal fixation
- Trochanteric fracture
- Damage to blood vessels
- Temporary or permanent nerve damage
- Subluxation or dislocation of the hip joint due to implant size or configuration selection, positioning of components and /or muscle and fibrous tissue laxity
- Lengthening or shortening of the affected extremity
- Breakage or chipping of the ceramic femoral head

#### EARLY POSTOPERATIVE

- Cardiovascular disorders including venous thrombosis, pulmonary embolism and myocardial infarction
- Hematoma and/or delayed wound healing
- Subluxation or dislocation

#### LATE POSTOPERATIVE

- Trochanteric avulsion from excessive muscular tension, weight-bearing, or inadvertent intraoperative weakening of the trochanter
- Aggravation of problems in the ipsilateral or contralateral knee and ankle joints due to leg length discrepancy, femoral medialization and/or muscular deficiencies.

- Femoral or acetabular fracture due to trauma or excessive loading particularly in the presence of poor bone stock caused by severe osteoporosis, bone defects from previous surgery, intraoperative reaming procedures, or bone resorption.
- Bone resorption which may contribute to the deterioration of fixation and eventual loosening of the implant
- Periarticular calcification or ossification which may lead to a decrease in joint mobility and range of motion
- Traumatic arthrosis of the ipsilateral knee secondary to intraoperative positioning of the extremity during surgery
- Subluxation or dislocation

## 5 PURPOSE

## 5.1 Primary Objective and Endpoint

The primary objective is to establish the mean superior cup migration of the PINNACLE® Dual Mobility Construct using model-based RSA over the first two years post-implantation. The primary endpoint is the mean vertical subsidence (Y translation, also known as superior cup migration) at 2 years as measured with RSA. Additionally, the data from this study will be compared to historical PINNACLE® data obtained in study DSJ\_2018\_02.

